9.4 GEMTUZUMAB OZOGAMICIN

(Mylotarg®, CDP-771, CMA-676, hP67.6-calicheamicin) NSC # 720568

Source and Pharmacology: Gemtuzumab ozogamicin is a combination of recombinant humanized anti-CD33 monoclonal antibody, conjugated with the cytotoxic antibiotic calicheamicin, isolated from fermentation of a bacterium, *Micromonospora echinospora* subsp. *calichensis*. The antibody portion of Gemtuzumab binds specifically to the CD33 antigen expressed on the surface of leukemic blasts and immature normal cells of myelomonocytic lineage, but not on normal hematopoietic stem cells. This antigen is expressed on the surface of leukemic blasts in more than 80% of patients with acute myeloid leukemia (AML). The binding of anti-CD33 antibody with the CD33 antigen results in the formation of a complex that is internalized, releasing the calicheamicin inside the lysosomes of the myeloid cell. The calicheamicin derivative binds to DNA in the minor growth groove, causing DNA double-strand breaks and cell death.

The first administration of a 9 mg/m² dose of gemtuzumab ozogamicin, given as a 2 hour infusion, results in elimination half-lives of total and unconjugated calicheamicin of about 41 and 143 hours, respectively. After the second 9 mg/m² dose, the half-life of total calicheamicin was increased to about 64 hours and the area under the concentration-time curve (AUC) was about twice that in the first dose period. The AUC for the unconjugated calicheamicin increased 30% after the second dose.

Toxicity:

	Common Happens to 21-100 children out of every 100	Occasional Happens to 5-20 children out of every 100	Rare Happens to <5 children out of every 100
Immediate: Within 1-2 days of receiving drug	Post infusion reaction (fever, chills, and rigors) dyspnea, headache, abdominal pain, asthenia, nausea, vomiting, anorexia, constipation, hypokalemia	Hypertension or hypotension, dizziness, tachycardia, back pain, diarrhea, dyspepsia, hypocalcemia, magnesemia, phosphatemia, anxiety, insomnia, depression	Anaphylaxis, hypoxia, hyperglycemia, tumor lysis syndrome
Prompt: Within 2-3 weeks, prior to the next course	Myelosuppression, increased liver enzymes, mucositis or stomatitis	Rash, pruritis, increased cough, infection, hemorrhage, hyperbilirubinemia, VOD (patients who receive gemtuzumab before or after HSCT) (L)	Intracranial bleed, DIC, GI bleed, VOD (L), ARDS (hypoxemia, pulmonary infiltrates, non-cardiogenic pulmonary edema) (L)
Delayed: Any time later during therapy, excluding the above conditions			
Late: Any time after completion of treatment			

Unknown Frequency and Timing: Fetal toxicities and teratogenic effects of gemtuzumab have been noted in animals at doses much higher than those used in humans. Toxicities include: decreased skeletal ossification, multiple anomalies, low birth weight and increased fetal mortality. It is not known if gemtuzumab is excreted into breast milk.

(L) Toxicity may occur later

Formulation and Stability: Available as single dose 5 mg amber vials of lyophilized powder. Store in the refrigerator at 2° to 8°C (36°-46° F), protected from light. Bring the vials to room temperature before diluting. Reconstitute vial contents with 5 mL of sterile water, and gently swirl the solution. Inspect the final solution for particulates. The reconstituted solution has a concentration of 1 mg/mL and is stable ≤ 8 hours if refrigerated and protected from light or ≤ 2 hours at room temperature prior to a 2-hour infusion.

Note: The product is very light sensitive. The vials should be diluted, and solution prepared, in a biologic safety cabinet with the fluorescent lights turned off.

Guidelines for Administration: See Treatment and Dose Modifications sections of the protocol.

Add appropriate dose to 100 mL of normal saline in either a polyvinyl chloride (PVC) or ethylene/polypropylene copolymer (non-PVC) IV bag covered by an ultraviolet (UV) light protector.

Gemtuzumab should only be diluted with 0.9% sodium chloride solution.

The diluted solution is stable ≤ 16 hours at room temperature prior to a 2-hour infusion.

Infuse over a 2-hour period in a peripheral or central line. **Do not give IV push or bolus.** Give through a separate IV line, using a 0.22 micron or 1.2-micron low protein-binding in-line filter.

Premedicate with acetaminophen and diphenhydramine and repeat every 4 hours as needed to prevent post-infusion symptom complex. Handle as with other cytotoxic agents. **Protect solution from light at all times.** Monitor vital signs during infusion and for 4 hours following infusion.

Supplier: Commercially available in the U.S. See package insert for further information.

9.5 ASPARAGINASE (ERWINIA CHRYSANTHEMI)

(*Erwinia chrysanthemi*, Erwinase®, ErwinazeTM, Crisantaspase)

Source and Pharmacology:

L-asparagine is a nonessential amino acid synthesized by the transamination of L-aspartic acid by a reaction catalyzed by the enzyme L-asparagine synthetase. Neoplastic cells associated with acute lymphoblastic leukemia, acute myeloid leukemia and lymphoblastic lymphosarcoma are asparagine-dependent but lack asparagine synthetase activity. The administration of L-asparaginase produces an anti-neoplastic effect by catalyzing asparagine into aspartic acid and ammonia. As a result, these cells lack the ability to produce the asparagine necessary for protein metabolism and survival. Deamination of glutamine may also play a role in the antineoplastic activity of asparaginase.

Asparaginase *Erwinia chrysanthemi* (Erwinase®) is asparaginase derived from cultures of *Erwinia chrysanthemi*. L-asparaginase is a tetrameric enzyme; each of the four identical subunits has a molecular weight of approximately 35 kDa. Asparaginase *Erwinia chrysanthemi* is immunologically distinct from *E. coli* L-asparaginase and may allow continued asparaginase therapy when a hypersensitivity reaction occurs to *Escherichia coli*-derived asparaginase. The package labeling states that there is insufficient information to characterize the incidence of antibodies to asparaginase *Erwinia chrysanthemi*. Several factors are involved in immunogenicity assay results and the assessment of antibodies, including assay methodology, assay sensitivity and specificity, sample handling, timing of sample collection, concomitant medications, and the underlying disease state. The following data have been reported on each of the three preparations of asparaginase:

Clinical Pharmacology of Asparaginase Formulation	Elimination half-life (IM)	% Anti-Asparaginase Antibody positive patients
Native Escherichia Coli	26-30 hours	45-75
Pegylated-asparaginase	5.5-7 days	5-18
Erwinia Asparaginase	16 hours (7-13 hrs package insert)	30-50

From: Avramis, V; Panosyan, E; Pharmacokinetic/Pharmacodynamic Relationships of Asparaginase Formulations: The Past, the Present and Recommendations for the Future. *Clin Pharmacokinet* 2005; 44 (4): 367-393.

Effective asparaginase levels have been defined as activity of ≥ 0.1 International Units per mL. Clinical trials with asparaginase *Erwinia chrysanthemi* demonstrated that 100% of patients achieved effective asparaginase levels at 48 and 72 hours (n=35 and n=13, respectively) following the third total dose when given on a Monday, Wednesday, Friday schedule using the IM route of administration. In a multicenter study characterizing the pharmacokinetic profile of 25,000 International Units/m² Erwinaze® given intravenously over one hour on the same dosing schedule of Monday, Wednesday, Friday for 2 consecutive weeks, 83% (20/24) and 43% (9/21) of evaluable patients achieved an asparaginase activity level of ≥ 0.1 International Units/mL at 48 post-dose 5 and 72 hours post-dose 6, respectively. No formal drug interaction studies have been performed with asparaginase *Erwinia chrysanthemi*.

Toxicity:

	Common Happens to 21-100 children out of every 100	Occasional Happens to 5-20 children out of every 100	Rare Happens to < 5 children out of every 100
Immediate: Within 1-2 days of receiving drug		Allergic reactions, anaphylaxis, urticaria	Local injection site reactions, fever
Prompt: Within 2-3 weeks, prior to the next course			Pancreatitis, glucose intolerance, thrombosis, hemorrhage, transient ischemic attack, disseminated intravascular coagulation, hyperbilirubinemia, alanine aminotransferase increased, aspartate aminotransferase increased, hyperglycemia, hyperammonemia, vomiting, nausea, abdominal pain, headache, diarrhea, seizure
Unknown Frequency and Timing:			Fetal toxicities and teratogenic effects of L-asparaginase have been noted in animals. It is unknown whether the drug is excreted in breast milk. Adequate, well-controlled studies of asparaginase Erwinia chrysanthemi have NOT been conducted. It is not known whether asparaginase Erwinia chrysanthemi will cause fetal harm or affect the ability to reproduce. It is not known if asparaginase Erwinia chrysanthemi is excreted into breast milk. The use of asparaginase Erwinia chrysanthemi should be avoided in pregnant or lactating patients.

(L) Toxicity may also occur later.

Formulation and Stability:

Asparaginase *Erwinia chrysanthemi* is supplied as a sterile, white lyophilized powder for reconstitution in a clear glass vial with a 3 mL capacity. Each vial contains 10,000 International Units of asparaginase *Erwinia chrysanthemi* and the following inactive ingredients: glucose monohydrate (5.0 mg), sodium chloride (0.5 mg). Store intact vials between 2°C and 8°C (36° to 46°F). Protect from light.

Guidelines for Administration: See Treatment and Dose Modification sections of the protocol. *Erwinia* asparaginase can be administered by intramuscular injection or by intravenous infusion. Use appropriate precautions for preparation of a hazardous agent. Visually inspect the powder in vial for foreign particles or discoloration prior to reconstitution.

For intramuscular administration, the contents of each vial should be reconstituted by slowly adding 1 mL or 2 mL of sterile, preservative-free NS to the inner vial wall. The final concentration is 10,000 International Units per mL when using 1 mL for reconstitution or 5,000 International Units per mL when using 2 mL for reconstitution. Gently mix or swirl the contents to dissolve the contents of the vial. Do not shake or invert the vial. The resulting solution should be clear and colorless. Discard if any particulate matter or protein aggregates are visible. **Withdraw the appropriate dosing volume into a polypropylene syringe within 15 minutes of reconstitution.** Polycarbonate luer-lok syringes from B-D (1 mL) are also acceptable (personal communication, EUSA Pharma). Discard any unused drug; do not save or use any unused drug remaining in the vial. No more than 2mL should be given at any one injection site. Doses larger than 2 mL should be divided and given in separate administration sites.

For intravenous use, slowly inject the appropriate volume of reconstituted solution into a Normal Saline 100 mL infusion bag; do not shake or squeeze the bag. Infuse *Erwinia* asparaginase over 1 hour. Do not infuse other intravenous drugs through the same intravenous line while infusing *Erwinia* asparaginase.

Administer the dose within a 4 hour time period from reconstitution. If the dose is not used within this time period, discard the dose. Do not freeze or refrigerate the reconstituted solution. Have available during and after the infusion: antihistamine, epinephrine, oxygen, and IV corticosteroids. Observe patient for ONE hour after administration for signs of hypersensitivity reactions.

9.6 SORAFENIB TOSYLATE

(BAY 43-9006 tosylate, BAY 54-9085 Nexavar®)

Source and Pharmacology: Sorafenib tosylate has the chemical name:

4-(4-{3-[4-Chloro-3-(trifluoromethyl) phenyl] ureido} phenoxy) *N*2-methylpyridine-2-carboxamide 4-methylbenzenesulfonate. Sorafenib is a kinase inhibitor that decreases tumor cell proliferation *in vitro*. Sorafenib was shown to inhibit multiple intracellular (CRAF, BRAF and mutant BRAF) and cell surface kinases (KIT, FLT-3, RET, VEGFR-1, VEGFR-2, VEGFR-3, and PDGFR- β). Several of these kinases are thought to be involved in tumor cell signaling, angiogenesis, and apoptosis. Sorafenib inhibited tumor growth and angiogenesis of human hepatocellular carcinoma, human renal cell carcinoma, and several other human tumor xenografts in immunocompromised mice.

The mean relative bioavailability of sorafenib administered as an oral tablet was 38–49% when compared to an oral solution. Pharmacokinetics studies in adults who received oral sorafenib showed that sorafenib reaches peak plasma levels in approximately 3 hours. When given with a moderate-fat meal (30% fat; 700 calories), the bioavailability was similar to that in the fasted state, however, with a high-fat meal (50% fat; 900 calories), sorafenib bioavailability was reduced by 29% compared to administration in the fasted state. Therefore, it is recommended that sorafenib be administered without food.

The mean maximum plasma concentration (C_{max}) and area under the concentration curve (AUC) increased less than proportionally when doses greater than 400 mg are given orally twice daily. *In vitro* binding of sorafenib to human plasma proteins is 99.5%. Sorafenib is metabolized mainly in the liver through oxidation by cytochrome P-450 (CYP) isoenzyme 3A4, and glucuronidation by uridine diphosphate-glucuronosyltransferase (UGT) 1A9. Sorafenib accounted for approximately 70–85% of the circulating analytes in plasma at steady state. Eight metabolites of sorafenib have been identified. The primary metabolite, a pyridine *N*-oxide derivative, is pharmacologically active, shows *in vitro* potency similar to that of sorafenib, and accounts for approximately 9–16% of total plasma concentrations of the drug. Approximately 77% of an oral dose of sorafenib is excreted in feces; 19% is eliminated in urine as glucuronidated metabolites. Unchanged sorafenib is recovered in feces and accounts for 51% of a single dose. No unchanged sorafenib is recovered in the urine.

The mean elimination half-life of sorafenib is approximately 25 to 48 hours. Multiple dosing of sorafenib for 7 days resulted in a 2.5 to 7-fold accumulation compared to single dose administration. Steady-state plasma sorafenib concentrations are achieved within 7 days, with a peak-to-trough ratio of mean concentrations of less than 2. A study of the pharmacokinetics of sorafenib indicated that the mean AUC of sorafenib in Asians (N=78) was 30% lower than the mean AUC in Caucasians (N=40). In adult patients, gender and age do not appear to have a clinically meaningful effect on the pharmacokinetics of sorafenib. In children with refractory solid tumors or leukemias, single agent sorafenib pharmacokinetics were similar to adults. Significant interpatient variability was observed both on Day 1 and at steady state. Drug exposure increased only marginally with dose escalation from 150 to 200 mg/m² for day 1 pharmacokinetics. The terminal half-life in children appeared to be prolonged (\geq 24 hours) but could not be estimated. Sorafenib accumulated after multiple doses and steady state appeared to be achieved after 5 to

7 days. Steady-state sorafenib concentrations (AUC_{0-12h/12}) were $4.1 \pm 2.1 \mu\text{g}/\text{mL}$ at the 150 mg/m² and $5.4 \pm 1.8 \mu\text{g}/\text{mL}$ at 200 mg/m² dose levels, respectively. The median apparent sorafenib clearance at the MTD was 56.0 mL/min/m². The apparent sorafenib clearance increased with patient age. The observed single agent sorafenib MTD in pediatric patients was 200 mg/m²/dose twice daily for solid tumors and 150 mg/m²/dose twice daily for leukemias. The pharmacokinetics of sorafenib in patients with varying degrees of renal and hepatic impairment have been studied. No dose adjustment is necessary in patients with renal impairment or with mild to moderate hepatic impairment.

Studies in human liver microsomes demonstrated that sorafenib competitively inhibited CYP2B6, CYP2C8, CYP2C9, CYP2C19, CYP2D6, and CYP3A4. However, sorafenib 400 mg twice daily for 28 days with substrates of CYP3A4, CYP2D6 and CYP2C19 did not increase the systemic exposure of these substrates. Studies with cultured human hepatocytes demonstrated that sorafenib did not increase CYP1A2 and CYP3A4 activities, suggesting that sorafenib is unlikely to induce CYP1A2 or CYP3A4 in humans. Drug interaction studies with the CYP3A4 inhibitor ketoconazole did not demonstrate a clinically important decrease in sorafenib exposure, however, the concentration of the active *N*-oxide metabolite decreased. Therefore, the use of strong or clinically relevant moderate CYP3A4 inhibitors should be avoided or used with caution. Continuous concomitant administration of sorafenib and rifampicin resulted in an average 37% reduction of sorafenib AUC. Other inducers of CYP3A4 activity (e.g., St. John's wort, phenytoin, carbamazepine, phenobarbital, and dexamethasone) may also increase the metabolism of sorafenib and thus decrease sorafenib concentrations. Please see Appendix II.

In vitro studies indicate that sorafenib inhibits glucuronidation by the uridine diphosphate-glucuronosyltransferase (UGT) 1A1 and 1A9 pathways. Systemic exposure to UGT 1A1 or 1A9 substrates may increase when co-administered with sorafenib. Caution is recommended when sorafenib is used concomitantly with drugs predominantly metabolized by the UGT 1A1 pathway such as irinotecan, whose active metabolite SN-38 is metabolized by UGT 1A1.

Sorafenib also inhibited P-glycoprotein *in vitro* and could increase the concentrations of concomitantly administered drugs that are P-glycoprotein substrates.

Concomitant use of docetaxel or doxorubicin with continuous sorafenib administration resulted in an increase in the AUC of both docetaxel and doxorubicin. With fluorouracil, both increases and decreases in AUC were seen. Therefore, caution is recommended when administering sorafenib with these chemotherapeutic drugs. Sorafenib does not appear to affect the metabolism of warfarin (a CYP2C9 substrate) *in vivo*; however, infrequent bleeding events or elevations of the International Normalized Ratio (INR) have been reported in some patients receiving concomitant therapy with warfarin. Patients taking concomitant warfarin should be monitored regularly for changes in prothrombin time, INR or clinical bleeding episodes.

Repeat dosing of sorafenib to young and growing dogs resulted in irregular thickening of the femoral growth plate at daily doses $\geq 600 \text{ mg}/\text{m}^2$ (approximately 0.3 times the AUC at the recommended human dose), hypocellularity of the bone marrow adjoining the growth plate at 200 mg/m²/day (approximately 0.1 times the AUC at the recommended human dose), and alterations of the dentin composition at 600 mg/m²/day. Similar effects were not observed in adult dogs when dosed for 4 weeks or less.

Toxicity

Adverse Events with Possible Relationship to Sorafenib (BAY 43-9006; Nexavar) (CTCAE 4.0 Term) [n= 2571]		
Likely (>20%)	Less Likely (<=20%)	Rare but Serious (<3%)
BLOOD AND LYMPHATIC SYSTEM DISORDERS		
Anemia		
CARDIAC DISORDERS		
		Acute coronary syndrome
	Chest pain - cardiac	
		Heart failure
		Left ventricular systolic dysfunction
		Myocardial infarction
GASTROINTESTINAL DISORDERS		
Abdominal pain		
	Ascites	
	Constipation	
Diarrhea		
	Gastrointestinal hemorrhage ²	
		Gastrointestinal perforation ³
	Mucositis oral	
Nausea		
	Vomiting	
GENERAL DISORDERS AND ADMINISTRATION SITE CONDITIONS		
	Edema limbs	
Fatigue		
	Fever	
HEPATOBILIARY DISORDERS		
		Hepatic failure
IMMUNE SYSTEM DISORDERS		
		Anaphylaxis
INFECTIONS AND INFESTATIONS		
	Infection ⁴	
INVESTIGATIONS		
	Activated partial thromboplastin time prolonged	
Alanine aminotransferase increased		
Alkaline phosphatase increased		
Aspartate aminotransferase increased		
Blood bilirubin increased		
Creatinine increased		
		Electrocardiogram QT corrected interval prolonged
INR increased	GGT increased	
	Investigations - Other (bicarbonate-serum low)	
Lipase increased		

Adverse Events with Possible Relationship to Sorafenib (BAY 43-9006; exa\lr) (CTCAE 4.0 Term) [n= 2571]		
Likely (≥20%)	Less Likely (<20%)	Rare but Serious (<3%)
Lymphocyte count decreased		
	Neutrophil count decreased	
Platelet count decreased		
Serum amylase increased		
Weight loss		
White blood cell decreased		
MEASUREMENTS AND NUTRITION DISORDERS		
Anorexia		
	Hypercalcemia	
Hyperglycemia		
	Hyperkalemia	
	Hypernatremia	
Hypoalbuminemia		
Hypocalcemia		
	Hypoglycemia	
	Hypokalemia	
Hyponatremia		
Hypophosphatemia		
MUSCULOSKELETAL AND CONNECTIVE TISSUE DISORDERS		
	Arthralgia	
	Back pain	
	Bone pain	
	Musculoskeletal and connective tissue disorder - Other (muscle spasm)	
	Myalgia	
	Pain in extremity	
NEOPLASMS BENIGN, MALIGNANT AND UNSPECIFIED (INCL CYSTS AND POLYPS)		
	Treatment-related secondary malignancy	
NERVOUS SYSTEM DISORDERS		
	Dizziness	
	Headache	
		Intracranial hemorrhage
		Reversible posterior leukoencephalopathy syndrome
PSYCHIATRIC DISORDERS		
	Insomnia	
RENAL AND URINARY DISORDERS		
	Acute kidney injury	
RESPIRATORY, THORACIC AND MEDIASTINAL DISORDERS		
	Cough	
	Dyspnea	
	Respiratory hemorrhage	
	Voice alteration	
SKIN AND SUBCUTANEOUS TISSUE DISORDERS		

Adverse Events with Possible Relationship to Sorafenib (BAY 43-9006; Nexavar) (CTCAE 4.0 Term) [n= 2571]		
Likely (>20%)	Less Likely (<=20%)	Rare but Serious (<3%)
Alopecia		
	Dry skin	
		Erythema multiforme
Palmar-plantar erythrodysesthesia syndrome		
	Pruritus	
Rash maculo-papular		
		Stevens-Johnson syndrome
		Toxic epidermal necrolysis
VASCULAR DISORDERS		
	Hypertension	
		Thromboembolic event

Formulation and Stability:

Sorafenib is supplied as a yellow-orange 50 mg and a red-colored 200 mg, round, immediate-release filmcoated tablet containing the excipients croscarmellose sodium, microcrystalline cellulose, hydroxypropylmethylcellulose, sodium lauryl sulfate, and magnesium stearate. The 200 mg film-coat consists of hydroxypropylmethyl cellulose, polyethylene glycol, titanium dioxide and red iron oxide. The 50 mg film-coat consists of hypromellose, PEG 3350, titanium dioxide, and yellow ferric oxide. The film coating has no effect on active BAY 43-9006 tosylate release rate.

Sorafenib 200 mg tablets are supplied in high-density polyethylene (HDPE) bottles of 140 tablets and the 50 mg tablets are supplied in HDPE bottles of 100 tablets. The bottles should be stored at controlled room temperature (15-25°C; 59-77°F) and storage temperature should not exceed 25°C (77°F). Stability testing is ongoing.

10.1 CRITERIA FOR REMOVAL FROM PROTOCOL THERAPY AND OFF STUDY CRITERIA

10.2 Criteria for Removal from Protocol Therapy

1. Failure to attain or maintain remission following Induction II ($\geq 5\%$ malignant blasts or extramedullary disease).
2. Relapse after Induction II of any site following remission.
3. Refractory CNS leukemia following 6 doses of IT cytarabine therapy in Induction I or Induction II.
4. CNS leukemia at start of Induction II after treatment for CNS leukemia in Induction I.
5. Grade 3 or greater neurotoxicity from HD cytarabine or,

6. Other intolerable or unacceptable toxicity secondary to the standard chemotherapy backbone.
7. Refusal of further protocol therapy by patient/parent/guardian.
8. Completion of planned therapy.
9. Physician determines it is in patient's best interest.
10. Development of a second malignancy.
11. Graft failure

Patients who are off protocol therapy are to be followed until they meet the criteria for Off Study (see below). Follow-up data will be required unless consent was withdrawn.

10.3 Off Study Criteria

1. Death.
2. Lost to follow-up.
3. Patient enrollment onto another study with tumor therapeutic intent (e.g., at recurrence).*
4. Withdrawal of consent for any further data submission.
5. Tenth anniversary of study entry.
6. Excluded constitutional condition or oncologic diagnosis is indicated following enrollment
7. FLT3/ITD status is unknown at End of Induction I.

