2.0 BACKGROUND

2.1 Introduction and rationale for development of chemotherapy backbone for de novo AML

Overall survival (OS) rates in pediatric acute myeloid leukemia (AML) approach 65-70% at three years with the current risk adapted chemotherapy and hematopoietic stem cell transplantation (HSCT) approach¹. The recently concluded Children's Oncology Group (COG) trial in pediatric de-novo AML AAML1031 (2011 – 2017) and its precursor trial AAML0531 (2006 – 2010) used a chemotherapy backbone adapted from the Medical Research Council (MRC) AML trials in order to improve overall outcomes²⁻⁴. This backbone comprised of an induction course of chemotherapy with cytarabine, daunorubicin and etoposide. Patients were risk stratified into low, intermediate and high risk groups on AAML0531 based on their cytogenetic and molecular features and their response at the end of this first cycle of induction chemotherapy¹. Patients on AAML0531 received 5 cycles of chemotherapy if they did not meet criteria for consideration of HSCT in first remission (Table 1). In addition, patients were randomized to receiving gemtuzumab ozogamicin (GO) at study entry and received this drug along with chemotherapy in Induction 1 and Intensification 2. Based on results from the MRC12 trial and preliminary analysis of AAML0531, the fifth course of chemotherapy was deleted from the chemotherapy backbone for AAML1031³. The risk stratification evolved over the years with the improvement in multi-dimensional flow cytometry (MDFC) and AAML1031 stratified patients into low and high risk categories using response defined by MDFC (measurement of minimal residual disease –MRD) in addition to cytogenetic and molecular features⁵.

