Patients with low-risk AML have favorable outcomes (3-year EFS and OS - 70% and 85% respectively) as compared to patients with high-risk AML (3-year EFS and OS – 30% and 48% respectively)¹. Regardless of risk, disease relapse still remains the major cause of mortality¹. Anthracyclines comprise an important component of relapsed AML therapy and higher doses of anthracyclines received in upfront AML therapy preclude their use at the time of relapse¹⁰. Given the concerns for long term toxicity without clear evidence of benefit to additional anthracyclines and etoposide in low-risk AML patients, we chose to adopt an institutional approach (Aflac-AML regimen) whereby newly diagnosed low-risk AML patients were treated with four cycles of chemotherapy that was identical to the high-risk group per AAML1031 which received chemotherapy alone. The aim of our regimen was to limit anthracycline exposure to 342 mg/m² and etoposide exposure to 1.25 g/m² in low-risk AML patients while maintaining the same favorable outcomes. A comparison of the two regimens is outlined in the table (Table 1) below.

Table 1: Therapy regimen for Aflac-AML, AAML0531 and AAML1031 low-risk patients

[figure not shown]
Aflac-AML		COG AAML0531		COG AAML1031	
Induction 1					
Cytarabine	100 mg/m ² /dose every 12 hours IV Days 1-10	Cytarabine	100 mg/m ² /dose every 12 hours IV Days 1-10	Cytarabine	100 mg/m ² /dose every 12 hours IV Days 1-10
Daunorubicin	50 mg/m ² /dose IV Days 1, 3, 5	Daunorubicin	50 mg/m ² /dose IV Days 1, 3, 5	Daunorubicin	50 mg/m ² /dose IV Days 1, 3, 5
Etoposide	100 mg/m ² /dose IV Days 1-5	Etoposide	100 mg/m ² /dose IV Days 1-5	Etoposide	100 mg/m ² /dose IV Days 1-5
Induction 2					
Cytarabine	1,000 mg/m ² /dose every 12 hours IV Days 1-4	Cytarabine	100 mg/m ² /dose every 12 hours IV Days 1-8	Cytarabine	100 mg/m ² /dose every 12 hours IV Days 1-8
Mitoxantrone	12 mg/m ² /dose IV Days 3-6	Etoposide	100 mg/m ² /dose IV Days 1-5	Etoposide	100 mg/m ² /dose IV Days 1-5
----	----	Daunorubicin	50 mg/m ² /dose IV Days 1, 3, 5	Daunorubicin	50 mg/m ² /dose IV Days 1, 3, 5
Intensification 1					
Cytarabine	1,000 mg/m ² /dose every 12 hours IV Days 1-5	Cytarabine	1,000 mg/m ² /dose every 12 hours IV Days 1-5	Cytarabine	1,000 mg/m ² /dose every 12 hours IV Days 1-5
Etoposide	150 mg/m ² /dose IV Days 1-5	Etoposide	150 mg/m ² /dose IV Days 1-5	Etoposide	150 mg/m ² /dose IV Days 1-5
Intensification 2					

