11.1 STATISTICAL CONSIDERATIONS

Sample size: This is a pilot study aimed at utilizing a risk-stratified approach along with pharmacogenomics to treat newly diagnosed patients with AML. Annually we expect to have 10-20 de novo AML patients to be diagnosed and treated at our institution. This two-year study would be expected to enroll approximately 30 patients (both low and high risk) during that time period. As a pilot study, this trial is not hypothesis-driven but rather estimation-driven, and the sample size is based on a feasible two-year target for our institution.

Descriptive statistics will be conducted for demographic and patient characteristic variables, including toxicity related variables. Mean and standard deviation will be used for continuous variables and frequency and percent will be used for categorical variables.

Primary Endpoints:

1. Event-free survival: Event-free survival (EFS) is defined as the time from on study to death, failure to achieve remission or relapse, where those patients who do not experience these events will be censored at last follow-up date. EFS will be estimated using the Kaplan-Meier method for newly diagnosed patients with pediatric acute myeloid leukemia using a risk stratified approach.

Secondary Endpoints:

1. Disease-free survival: Disease-free survival (DFS) from end of first course of therapy is defined as time from end of first course of therapy to death or relapse, where those patients who do not experience these events will be censored at last follow-up date. DFS will be estimated using the Kaplan-Meier method for newly diagnosed patients with pediatric acute myeloid leukemia using a risk stratified approach.
2. Overall survival: Overall survival (OS) is defined as (1) time from study entry and (2) from end of first course of therapy to death, where those who do not die will be censored at

last follow-up date. OS will be estimated using the Kaplan-Meier method for newly diagnosed patients with pediatric acute myeloid leukemia using a risk stratified approach.

3. Minimal residual disease: Minimal residual disease (MRD) is the proportion of patients that are in remission (MRD negative) after one cycle of induction chemotherapy in both the GO and non-GO groups. Descriptive statistics (frequency and percent) will be used to estimate the frequency of MRD.

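### Overall survival follow-up stops when a patient joins another therapeutic study, so Kaplan-Meier OS is biased upward to the extent that relapsed patients leave this way

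*Combined protocol and SAP*

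**What the plan says.** Section 10.2 sets the follow-up rule: "Patients who are off protocol therapy are to be followed until they meet the criteria for Off Study". The next sentence adds "Follow-up data will be required unless consent was withdrawn".

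Section 10.3 lists the off-study criteria. Criterion 3 is "Patient enrollment onto another study with tumor therapeutic intent (e.g., at recurrence"), followed by an asterisk with no matching footnote in the text available. The list also includes death, loss to follow-up, withdrawal of consent for further data submission, and "Tenth anniversary of study entry".

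Section 11.1 defines OS from two origins, study entry and end of the first course, "where those who do not die will be censored at" the last follow-up date, and estimates it by Kaplan-Meier. It gives no sensitivity analysis for early departure, and no section asks for vital status after a patient goes off study.

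OS is the first secondary objective (Section 1.2). On prognosis, Section 2.1.1 states: "Regardless of risk, disease relapse still remains the major cause of mortality".

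**The concern.** Kaplan-Meier treats a censored patient as having the same future death hazard as those still under observation. Criterion 3 gives recurrence as its own example, so the patients it removes are largely those whose death hazard has just risen. Their later deaths are not counted, and the patients who remain at risk are a healthier group. OS is then overestimated from both time origins.

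The protocol quotes 3-year OS for comparable populations (Section 2.1: "approach 65-70% at three years with the current risk adapted chemotherapy"; Section 2.1.1: 85% low risk, 48% high risk). A reader will set the trial's OS beside those figures, and part of any advantage could come from the follow-up rule. In a trial that describes itself as estimation-driven, the estimate is the product, and enrolling more patients would not remove this bias.

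**Working it through.** **Inputs from the documents.**
- Sample size about 30 (Section 11.1). This reproduces: 10-20 patients a year × 2 years = 20-40, midpoint 30.
- All AML: EFS about 50%, OS about 65% (opening summary, no time point given; treated here as 3-year values, since Section 2.1 gives OS of 65-70% at three years).
- High risk: 3-year EFS 30%, OS 48%. Low risk: 70%, 85% (Section 2.1.1).

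**Assumptions, not in the documents.** Constant hazards; a share s = 0.8 to 0.9 of first events are relapses and the rest are deaths; a fraction f of relapsed patients enrol elsewhere, at relapse or after an exponential delay with mean 2 months; leaving is unrelated to prognosis (relaxed below).

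**Model.**
1. First-event hazard: λ = −ln(EFS)/3. All AML: −ln(0.50)/3 = 0.231 per year.
2. True OS(t) = e^(−λt) + sλ(e^(−μt) − e^(−λt))/(λ − μ), solved for the post-relapse death hazard μ that gives the quoted OS at t = 3. All AML: μ = 0.693 (s = 0.8) or 0.797 (s = 0.9). Check for s = 0.8: 0.50 + 0.8 × 0.231 × (0.125 − 0.50)/(0.231 − 0.693) = 0.50 + 0.15 = 0.65.
3. With leaving at relapse, the relapsed patients still observed are R(t) = (1 − f)sλ(e^(−μt) − e^(−λt))/(λ − μ). The observed death hazard is h(t) = [(1 − s)λe^(−λt) + μR(t)]/[e^(−λt) + R(t)].
4. Kaplan-Meier tends to exp(−∫h(t)dt) over 0 to 3 years. At f = 0 it returns the true OS.

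**3-year OS as it would read** (range over s = 0.8 to 0.9; 2-month mean delay in brackets):

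| Population, true OS | f = 10% | f = 25% | f = 50% |
|---|---|---|---|
| All AML, 65% | 66.6-67.0% (66.4-66.7%) | 69.2-70.2% (68.5-69.3%) | 74.2-76.5% (72.6-74.3%) |
| High risk, 48% | 49.8-50.2% (49.5-49.8%) | 52.8-53.9% (52.0-52.9%) | 58.9-61.8% (56.9-59.1%) |
| Low risk, 85% | 85.7-86.0% (85.6-85.8%) | 86.8-87.5% (86.5-87.1%) | 88.7-90.2% (88.2-89.4%) |

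**In patients.** For all AML the number leaving by 3 years is 30 × 0.50 × s × f: 1.2-1.4, 3.0-3.4 and 6.0-6.8 at f = 10%, 25% and 50%.

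**Against sampling error.** SE at 65% with n = 30 is √(0.65 × 0.35/30) = 0.087. A simulation with n = 30, s = 0.9 and leaving one month after relapse gave mean OS of 64.7%, 69.5% and 75.2% at f = 0, 25% and 50%, with a standard deviation of about 8.6 points.

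**If leavers have a better prognosis.** With s = 0.9 and a one-month delay, OS reads 69.7% at f = 25% and 75.3% at f = 50%. If leavers have half the post-relapse hazard of those who stay, it reads 68.1% and 73.1%. The bias shrinks but remains upward.

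**The case against.** The strongest objection is the asterisk. Criterion 3 is the only off-study criterion that carries one, so a qualifying note may exist for exactly this line and may have been lost when the PDF was read. This stands as a limit: nothing shows what the note says, and if it provides for survival follow-up there is no bias to correct.

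The requirement for follow-up data unless consent is withdrawn can be read as having no other exception. But it comes directly after the sentence that ends follow-up at the off-study point and concerns patients off protocol therapy. Withdrawal of consent is also a separate criterion (number 4), so criterion 3 ends follow-up without it. If the wording is thought ambiguous, that too calls for a clarification. In a single-centre trial some later deaths may become known anyway; this limits the likely size, but nothing requires that they be collected.

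The fraction leaving, the delay and the relapse share are all assumed, and this stands. Section 11.1 also does not clearly plan OS by risk group; if groups are reported, 8.7 points is the wrong yardstick (with an assumed 15 high-risk patients at 48%, √(0.48 × 0.52/15) = 12.9 points).

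Finally, OS is secondary, no decision rule uses it, and EFS already counts relapse as an event. All of this is true and bears on priority. It does not make the OS estimate correct.

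**Conclusion.** The concern holds on the text available. Followed as written, the rules censor relapsed patients when they join another therapeutic study and bias OS upward. The direction needs only that leavers have a higher death hazard than the patients who remain, which the protocol's own statement on relapse supports.

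The size is not established. It is zero if nobody leaves. For all AML it is about 1-2 points at 10% leaving, 4-5 at 25% and 8-12 at 50%, across the delay and relapse-share assumptions used. Only the last reaches about one standard error. It should be fixed because the error is one-directional, invisible in a confidence interval and hard to repair later if vital status was not collected. Confidence is moderate, because of the missing footnote.

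**What to change.** - **Footnote.** Supply the note for the asterisk on criterion 3. If it already provides for survival follow-up, repeat it in Section 11.1 and change nothing else.
- **Section 10.3.** Otherwise, state that enrolment on another therapeutic study ends protocol therapy and toxicity collection only. Vital status and date of first relapse continue to be collected until death, loss to follow-up, withdrawal of consent for data submission, or the tenth anniversary. The relapse date matters because recurrence is only an example in criterion 3, and a patient who leaves before relapse would otherwise be lost to EFS and DFS as well.
- **Section 11.1.** State that OS is censored at the date last known alive, regardless of enrolment on another study, and report how many patients enrolled elsewhere.

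With vital status collected in this way, the bias in the model is zero. The cost is one sentence in each section, submitted as an amendment, and periodic vital-status and relapse checks for about 30 patients at one centre. The consent must cover this follow-up, which could not be checked here because the consent pages were not available. No treatment or clinical rule changes.
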